## **1.0 STUDY SUMMARY**

|  |   |
|--|---|
| Name of sponsor:
Millennium Pharmaceuticals, Inc, a wholly owned subsidiary of Takeda Pharmaceutical Company Limited
Please note: Millennium Pharmaceuticals, Inc, a wholly owned subsidiary of Takeda Pharmaceutical Company Limited, may be referred to in this protocol as "Millennium," "sponsor," or "Takeda".   | Compound:
TAK-954               |
| Study Identifier: TAK-954-1005  | Phase: 1                           |
| Protocol Title: A Phase 1, Open-label, Single Intravenous Infusion Dose Study to Evaluate the Mass Balance, Pharmacokinetics, Metabolism, and Excretion of TAK-954 Containing Microtracer ( $[^{14}\text{C}]\text{-TAK-954}$ ) in Healthy Adult Male Subjects   |   |
| Trial Design:
This is a phase 1, open-label study in 6 healthy male subjects. The study will include a screening visit, a treatment period, and a follow-up period. At least 6 subjects will be dosed in the study.
Subjects will complete the screening visit within approximately 28 days before study drug administration.
Eligible subjects will be enrolled into the study and will receive a single 60-minute intravenous (IV) infusion of 0.5 mg TAK-954 containing a microtracer of $[^{14}\text{C}]\text{-TAK-954}$ (~1.5 $\mu\text{Ci}$ ).
Subjects will be confined from admission for a minimum of 7 days. If the recovery of radioactivity has not met the target conditions specified below, a subject's duration of confinement may be maximally extended to Day 15 (336 hours postdose). Should the duration of confinement be extended, clinical assessments planned at discharge will be rescheduled accordingly.
An individual subject will be discharged from the clinic when at least 1 of the following criteria has been met for that subject:
1. $\geq 90\%$ of the administered radioactivity has been recovered in excreta.
2. Excreta samples from 2 consecutive days contain $< 1\%$ of the administered radioactivity.
Safety will be assessed by monitoring for adverse events (AEs), vital signs, electrocardiograms (ECGs), clinical laboratory results, and physical examinations. |   |
| Trial Primary Objective:
The primary objectives of the study are: 

To determine the mass balance and routes of elimination of a single IV dose of TAK-954 containing microtracer (<math>[^{14}\text{C}]\text{-TAK-954}</math>).

To characterize the metabolic profiles following single-dose IV administration of TAK-954 containing microtracer (<math>[^{14}\text{C}]\text{-TAK-954}</math>) and identify major circulating and excreted metabolites.

To determine the single-dose pharmacokinetics (PK) of total radioactivity, TAK-954, THRX513466, and THRX 913682, where possible.

  |   |
| Secondary Objectives:
The secondary objective of the study is to evaluate the safety and tolerability of a single IV dose of TAK-954 containing microtracer ( $[^{14}\text{C}]\text{-TAK-954}$ ) in healthy male subjects.   |   |
| Trial Subject Population: Healthy male subjects, aged 18 to 55 years, inclusive.  |   |
| Planned Number of Subjects:
At least 6 subjects  | Planned Number of Sites:
1 site |

|  |  |
|--|--|
| Dose Level:
0.5 mg TAK-954 IV containing a microtracer of [14C]-TAK-954 (~1.5 $\mu$ Ci). | Route of Administration:
IV                              |
| Duration of Treatment:
Single dose   | Planned Trial Duration:
Up to approximately 6 to 7 weeks |

**Main Criteria for Inclusion:**

To be eligible for study participation, subjects must:

- Be a man aged 18 to 55 years, inclusive, at the screening visit.
- Have a body mass index  $\geq 18$  and  $\leq 30$  kg/m^2 and a body weight  $> 50$  kg at the screening visit.
- Be a nonsmoker who has not used tobacco- or nicotine-containing products (eg, nicotine patch) for at least 6 months before administration of the initial dose of trial drug.
- Be judged to be in good health by the investigator on the basis of clinical evaluations including laboratory safety tests, medical history, physical examination, 12-lead ECG, and vital sign measurements performed at the screening visit and before administration of the initial dose of trial drug.
- Meet the following birth control requirements:
  - Is a male subject who is sterile or agrees to use an appropriate method of contraception, including a condom, from the first dose of study drug until 30 days after the last dose of study drug. No restrictions are required for a vasectomized male subject provided that the subject is at least 1 year postbilateral vasectomy procedure before the first dose of study drug. A male subject whose vasectomy procedure was performed less than 1 year before the first dose of study drug must follow the same restrictions as a nonvasectomized man. Appropriate documentation of surgical procedure should be provided.
  - Is a male subject who agrees to not donate sperm from trial drug administration on the first day of the first dose until 30 days after the last dose of study drug.

**Main Criteria for Exclusion:**

The subject must be excluded from participating in the study if the subject:

- Has participated in another investigational trial within 4 weeks (or based on local regulations) before the pretrial visit (screening). This window will be derived from the date of the last trial procedure or AE related to the trial procedure in the previous trial to the pretrial/screening visit of the current trial.
- Has total C radioactivity measured by accelerator mass spectrometry in plasma (during screening) exceeding C/C ratio 1.1E.
- Participated in any study with a radiation dose above 0.1 MBq or radiation burden above 0.1 mSv within 1 year before screening.
- Was exposed to significant radiation (eg, serial x-ray or computed tomography scans, barium meal, current employment in a job requiring radiation exposure monitoring) within 12 months before check-in.
- Irregular defecation pattern (less than once per 2 days).

**Main Criteria for Evaluation and Analyses:**

The primary endpoints of the study are:

1. Percentage of administered radioactive dose recovered in urine and feces and cumulative recovery in urine and feces combined.
2. TAK-954 and metabolites (if any) expressed as a percentage of total radioactivity in plasma and as a percentage of dose in urine and in feces.
3. Concentration of total radioactivity in whole blood and plasma.
4. PK parameters to describe the single-dose PK, postdose on Day 1, for a) total radioactivity in whole blood and plasma, b) TAK-954 in plasma, c) THRX513466 and THRX 913682 in plasma (where possible):

- Maximum observed concentration ( $C_{\max}$ ).
- Area under the concentration-time curve from time 0 to time of the last quantifiable concentration ( $AUC_{\text{last}}$ ).
- Area under the concentration-time curve from time 0 to infinity ( $AUC_{\infty}$ ).
- Time of first occurrence of  $C_{\max}$  ( $t_{\max}$ ).
- $t_{1/2z}$ .
- Total clearance after IV administration (TAK-954 only).
- Volume of distribution during the terminal disposition phase after IV administration ( $V_z$ ) (TAK-954 only).
- Amount of total radioactivity and TAK-954 excreted in urine and radioactivity only for feces from 0 to time  $t$  ( $A_{\text{et}}$ ).
- Fraction of TAK-954 dose and total radioactivity excreted in urine and radioactivity only for feces from time 0 to time  $t$  ( $f_{\text{et}}$ ).

Secondary endpoints include:

1. The ratio of total radioactivity in whole blood and plasma.
2. The ratio of plasma TAK-954 to total radioactivity in plasma.
3. Safety:
  - Percentage of subjects who experience at least 1 treatment-emergent AE.
  - Percentage of subjects who discontinue because of an AE.

#### **Statistical Considerations:**

#### **Concentration Data:**

Plasma concentration of TAK-954 and its metabolites and total radioactivity in whole blood and plasma at each scheduled timepoint will be summarized using descriptive statistics. Mass balance will be assessed by the percentage and cumulative percentage of administered radioactive dose recovered in urine and in feces and their combined total at appropriate intervals. Descriptive statistics will be used.

Mean and individual cumulative excretion of radioactivity in urine and in feces and their combined total by time curve will be displayed.

Individual percentage and cumulative percentage will be presented in data listings.

All concentration data will be listed.

#### **PK:**

[figure not shown]
Descriptive statistics will be used to summarize the PK parameters. All PK parameter data will be listed. Statistical analyses will be performed if appropriate.

Circulatory and excretory metabolite profiles will be established for each subject. Metabolites will be presented as a mean percentage of total radioactivity and/or dose. Descriptive statistics will be used.

#### **Sample Size Justification:**

The sample size ( $n = 6$ ) is based on the consideration that radioactivity is being administered to healthy subjects and that generally 6 subjects is sufficient to characterize the endpoints described in the protocol and is accepted by regulatory agencies.

## **2.0 STUDY SCHEMATIC**

Abbreviation: IV, intravenous.

## 3.0 SCHEDULE OF STUDY PROCEDURES

| Assessment  | Screening      | Trial Days     |                                 |    |    |    |     |     |     |         |   |      | Follow-up/
Early
Termination |
|---|----------------|----------------|---------------------------------|----|----|----|-----|-----|-----|---------|---|------|------------------------------------|
|   |                | -28 to -2      | -1                              | 1  | 2  | 3  | 4   | 5   | 6   | 7       | 8 | 9-15 |                                    |
| Day   | Hours Postdose | 0              | 24                              | 48 | 72 | 96 | 120 | 144 | 168 | 192-336 |   |      |                                    |
| Administrative Procedures  |                |                |                                 |    |    |    |     |     |     |         |   |      |                                    |
| Informed consent  | X              |                |                                 |    |    |    |     |     |     |         |   |      |                                    |
| Inclusion/exclusion criteria  | X              | X              |                                 |    |    |    |     |     |     |         |   |      |                                    |
| Medication history  | X              |                |                                 |    |    |    |     |     |     |         |   |      |                                    |
| Prior and concomitant medication review   |                |                | -----Continuous monitoring----- |    |    |    |     |     |     |         |   |      |                                    |
| Clinic Procedures/Assessments  |                |                |                                 |    |    |    |     |     |     |         |   |      |                                    |
| Full physical exam  | X              | X a |                                 |    |    |    |     |     |     |         |   |      | X                                  |
| Semirecumbent vital signs (heart rate, systolic blood pressure, and diastolic blood pressure) | X              |                | X b                  | X  |    |    |     |     |     |         |   |      | X                                  |
| Vital signs (respiratory rate and oral or tympanic temperature)                               | X              |                | X b                  |    |    |    |     |     |     |         |   |      | X                                  |
| Height  | X              |                |                                 |    |    |    |     |     |     |         |   |      |                                    |
| Weight  | X              | X              |                                 |    |    |    |     |     |     |         |   |      |                                    |
| Body mass index   | X              |                |                                 |    |    |    |     |     |     |         |   |      |                                    |
| Standard 12-lead electrocardiogram  | X              |                | X b                  | X  |    |    |     |     |     |         |   |      | X                                  |
| Adverse event monitoring  |                |                | -----Continuous monitoring----- |    |    |    |     |     |     |         |   |      |                                    |
| Laboratory Procedures/Assessments  |                |                |                                 |    |    |    |     |     |     |         |   |      |                                    |
| Serum chemistry   | X              | X a |                                 |    |    |    |     |     |     |         |   |      | X                                  |
| Hematology  | X              | X a |                                 |    |    |    |     |     |     |         |   |      | X                                  |
| Urinalysis  | X              | X a |                                 |    |    |    |     |     |     |         |   |      | X                                  |
| Urine drug screen   | X              | X a |                                 |    |    |    |     |     |     |         |   |      |                                    |
| Alcohol screen  | X              | X a |                                 |    |    |    |     |     |     |         |   |      |                                    |
| HIV test  | X              |                |                                 |    |    |    |     |     |     |         |   |      |                                    |

CONFIDENTIAL

| Assessment   | Screening      | Trial Days |        |    |    |    |     |     |     |         |                |                | Follow-up/
Early
Termination |
|--|----------------|------------|--------|----|----|----|-----|-----|-----|---------|----------------|----------------|------------------------------------|
|  |                | -28 to -2  | -1     | 1  | 2  | 3  | 4   | 5   | 6   | 7       | 8              | 9-15           |                                    |
| Day  | Hours Postdose | 0          | 24     | 48 | 72 | 96 | 120 | 144 | 168 | 192-336 |                |                |                                    |
| Hepatitis panel  | X              |            |        |    |    |    |     |     |     |         |                |                |                                    |
| Pharmacokinetics (PK) Evaluations   |                |            |        |    |    |    |     |     |     |         |                |                |                                    |
| Blood collection for total radioactivity in whole blood and plasma, TAK-954 in plasma, and metabolite profiling c |                |            | X----- |    |    |    |     |     |     |         |                |                |                                    |
| Urine collection for total radioactivity, TAK-954 concentrations, and metabolite profiling d                      |                | X          | X----- |    |    |    |     |     |     |         |                |                |                                    |
| Emesis e  |                |            | X      |    |    |    |     |     |     |         |                |                |                                    |
| Feces collection for total radioactivity and metabolite profiling f   |                | X          | X----- |    |    |    |     |     |     |         |                |                |                                    |
| Total  C radioactivity measured by accelerator mass spectrometry (AMS) in plasma.                               | X              |            |        |    |    |    |     |     |     |         |                |                |                                    |
| Drug Administration   |                |            |        |    |    |    |     |     |     |         |                |                |                                    |
| [  C]-TAK-954 dosing  |                |            | X      |    |    |    |     |     |     |         |                |                |                                    |
| Other   |                |            |        |    |    |    |     |     |     |         |                |                |                                    |
| Confinement  |                | X          | X      | X  | X  | X  | X   | X   | X   | X       | X g | X g |                                    |

a Within 24 hours before dosing on Day 1.b Assessments predose (between waking up and the start of the infusion) and at the end of the infusion.c PK blood samples (for total radioactivity in whole blood and plasma and TAK-954 in plasma) are collected predose (within 30 minutes) and at 0.5, 1 (at end of infusion), 1.5, 2, 3, 4, 6, 12, 24, 36, 48, 72, 96, 120, 144, and 168 hours postdose and every 24 hours thereafter while the subject is confined. Blood samples for metabolite profiling will be collected predose and at 1 (at end of infusion), 2, 4, 8, 12, 24, 48, 72, 96, 120, 144, and 168 hours postdose and every 24 hours thereafter while the subject is confined.d Urine will be collected predose (spot sample -12 to 0 hours) and at 0-6, 6-12, 12-24, 24-48, 48-72, 72-96, 96-120, 120-144, and 144-168 hours and every 24 hours thereafter while the subject is confined.e If emesis occurs within 8-10 hours after dosing, vomitus will be collected in a preweighed container assigned to each subject, reweighed, and submitted for analysis of total radioactivity.f Feces will be collected predose (last stool before dosing), and all samples produced up to at least 168 hours postdose (to be pooled in 24-hour intervals) and every

24 hours thereafter will be collected while the subject is confined.

g Subjects will be confined only if requirements for discharge are not met.

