## **6.0 TRIAL DESIGN AND DESCRIPTION**

### **6.1 Trial Design**

This is a phase 1, open-label study in 6 healthy male subjects. The study will include a screening visit, a treatment period, and a follow-up period. At least 6 subjects will be dosed in the study. The site should have alternate subjects available on the dosing day in case a subject is discontinued on Day 1.

Subjects will complete the screening visit within approximately 28 days before study drug administration.

Eligible subjects will be enrolled into the study and will receive a single 60-minute IV infusion of 0.5 mg TAK-954 containing a microtracer of [C]-TAK-954 (~1.5 µCi). For standardization purposes, study drug will be administered following at least 2 hours of fasting.

Subjects will be confined from admission for a minimum of 7 days. If the recovery of radioactivity has not met the target conditions specified below, a subject's duration of confinement may be maximally extended to Day 15 (336 hours postdose). Should the duration of confinement be extended, clinical assessments planned at discharge will be rescheduled accordingly.

An individual subject will be discharged from the clinic when at least 1 of the following criteria has been met for that subject:

1. ≥90% of the administered radioactivity has been recovered in excreta.
2. Excreta samples from 2 consecutive days contain <1% of the administered radioactivity.

Discharge/stopping criteria will be assessed daily by liquid scintillation counting or using AMS until target conditions have been met, but ultimately, a subject's duration of confinement will not extend beyond Day 15 (336 hours postdose).

Specific measures should be taken to prevent the subject from missing a fecal or urine collection by strictly controlling and providing access to designated restrooms only.

Safety will be assessed by monitoring for AEs, vital signs, ECGs, clinical laboratory results, and physical examinations.

Follow-up visit procedures will be performed on the last possible day (15 days after the start of the infusion) of discharge; subjects who meet the stopping criteria before this day will be asked to return for a follow-up visit on Day 15 (±2 days).

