### **6.2 Rationale for Trial Design, Dose, and Endpoints**

#### **6.2.1 Rationale for Trial Design**

This trial has a standard design for assessing mass balance, metabolic profiles, and routes of elimination. The duration of sampling was chosen on the basis of the plasma elimination half-life for the parent drug (approximately 19 hours in healthy subjects), and observations from nonclinical tissue distribution and mass-balance studies.

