## **6.3 Trial Design/Dosing/Procedure Modifications Permitted Within Protocol Parameters**

This is a phase 1 assessment of TAK-954 in humans, and the PK, pharmacodynamic, and safety profiles of the compound are still being elucidated. This protocol is written with some flexibility to

accommodate the inherent dynamic nature of phase 1 clinical trials. Modifications to the clinical or laboratory procedures currently outlined below may be required to achieve the scientific goals of the trial objectives or to ensure appropriate safety monitoring of the trial subjects.

Up to an additional 50 mL of blood may be drawn. The total blood volume withdrawn from any single subject will not exceed the total maximum allowable volume during the subject's participation in the trial.

It is understood that the current trial may employ some or none of the alterations described above. Any alteration made to this protocol to meet the trial objectives must be detailed by the sponsor in a letter to the trial master file and forwarded to the investigator for retention. The letter may be forwarded to the institutional review board (IRB)/independent ethics committee (IEC) at the discretion of the investigator.

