### **11.3 Determination of Sample Size**

No formal sample size calculations have been performed. The sample size ( $n = 6$ ) is based on the consideration that radioactivity is being administered to healthy subjects and that generally 6 subjects is sufficient to characterize the endpoints described in the protocol and is accepted by regulatory agencies.

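### Blood sampling for total radioactivity stops at an excreta-triggered discharge, so a slow terminal phase could be seen but not reliably estimated; one sample at the existing Day 15 visit would be a cheap safeguard

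*Protocol*

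**What the plan says.** Protocol Section 5.2.1 and SAP Section 5.1 list half-life and AUC to infinity of total radioactivity, in whole blood and plasma, among the primary endpoints.

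Footnote c of the schedule (Protocol Section 3.0, repeated in SAP Appendix A) sets the blood times for radioactivity up to "168 hours postdose and every 24 hours thereafter while the subject is confined". Sampling after 168 h therefore lasts only as long as the stay in the clinic.

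Protocol Section 6.1 (also 9.3.2, and SAP Section 4.3) sets the length of stay: "Subjects will be confined from admission for a minimum of 7 days", extendable to Day 15 (336 h). "An individual subject will be discharged from the clinic when at least 1 of the following criteria has been met for that subject". The two criteria are:

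- "≥90% of the administered radioactivity has been recovered in excreta"
- "Excreta samples from 2 consecutive days contain <1% of the administered radioactivity"

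The second has no recovery floor and does not say whether the 1% applies to each day or to both days together. Neither criterion refers to blood.

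Subjects discharged early return on Day 15 (±2 days). Chemistry and hematology are scheduled at that visit, but no radioactivity sample.

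On the length of sampling, Protocol Section 6.2.1 says: "The duration of sampling was chosen on the basis of the plasma elimination half-life for the parent drug". It gives about 19 h, and the same sentence goes on to cite nonclinical tissue-distribution and mass-balance findings. No half-life for total radioactivity is given.

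**The concern.** The excreta rule decides when blood sampling ends, yet the blood curve has its own primary endpoints. A subject released on the second criterion alone has more than 10% of the dose unaccounted for and very little coming out. Either the remainder is still in the body and leaving slowly, or excreta were lost, or the two days happened to contain little stool. A late blood concentration helps to separate the first explanation from the others. In that subject, however, blood sampling may already have ended at 168 h. His total-radioactivity half-life and AUC to infinity would then be the least certain in the trial, in the subject where they matter most for interpreting the mass balance.

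**Working it through.** The documents give no half-life for total radioactivity and no precision target, so there is no stated figure to reproduce.

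Inputs from the documents: last blood sample between 168 h and 336 h (footnote c and Section 6.1; 168 h is taken as the earliest because footnote c lists it unconditionally); thresholds of 90% and 1% (Section 6.1); parent half-life 19 h (Section 6.2.1). Assumptions: first-order loss, the whole shortfall retained, residual CVs of 5%, 10% and 20%, and a slow-phase intercept of 1% to 10%.

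**Step 1. Radioactivity behaves like the parent.** 168/19 = 8.8 half-lives, and 2^(−8.8) leaves about 0.2%. There is no problem in this case.

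**Step 2. Implied half-life after release on criterion 2.** Take 10% of dose retained and just under 1% excreted.

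- 1% per day: k = 1/10 = 0.1 per day, so half-life = 0.693/0.1 = 6.93 days = 166 h. Counting the loss over the two days instead, k = ln(12/10)/2, gives 7.60 days = 182 h.
- 1% over both days: k = 0.5/10 = 0.05 per day gives 13.9 days = 333 h; k = ln(11/10)/2 gives 14.5 days = 349 h.

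These are minimum values under the assumptions, because the shortfall exceeds 10% and the output is below 1%. At 80% recovery on the per-day reading, k = 1/20 gives 333 h.

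**Step 3. Half-lives covered, at 90% recovery.**

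| Reading of the 1% | Last sample 168 h | Last sample 336 h |
|---|---|---|
| Per day (166-182 h) | 0.92-1.01 | 1.84-2.02 |
| Two days combined (333-349 h) | 0.48-0.50 | 0.96-1.01 |

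**Step 4. Precision of the terminal slope.** For a log-linear fit, SE(k) = CV/√Σ(d − d̄)², with d in days. Take a true k = ln(11/10) = 0.0953 per day (7.3 days) and a CV of 10%.

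- Samples at 72, 96, 120, 144 and 168 h: Σ = 10, SE = 0.0316, t(3 df) = 3.182. The CI for k is −0.005 to 0.196, so the half-life is 3.5 days to unbounded.
- One sample added at 336 h: mean 6.5 days, Σ = 77.5, SE = 0.0114, t(4 df) = 2.776. The CI for k is 0.064 to 0.127, so the half-life is 5.5 to 10.9 days.
- At 5% CV the interval goes from 4.8-15.4 to 6.2-8.7 days. At 20% it goes from 2.3 days-unbounded to 4.4-21.5 days.
- For a true 19 h half-life, the 72-168 h samples at 10% CV give k = 0.876 ± 0.101 per day, or 17.0 to 21.5 h. This does not overlap the slow case, whose lower limit is 3.5 days.

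**Step 5. Share of AUC to infinity beyond the last sample.** Let C(t) be proportional to 2^(−t/19) + b·2^(−t/166). The slow phase's share of total AUC is 166b/(19 + 166b): 1.66/20.66 = 8.0% for b = 0.01 and 16.6/35.6 = 46.6% for b = 0.10. The fraction of the slow phase beyond 168 h is 2^(−168/166) = 0.496, and beyond 336 h it is 0.246. So about 4% to 23% of AUC to infinity lies beyond 168 h, and about 2% to 11% beyond 336 h.

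**Limit of step 4.** It assumes that every sample from 72 h lies on the slow phase. In the step 5 model the two phases are equal at log2(1/b)/(1/19 − 1/166) hours: 71 h for b = 0.10 and 143 h for b = 0.01. With a small intercept, fewer scheduled samples describe the slow phase, and its half-life is harder to estimate than step 4 shows.

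**The case against.** The strongest reply is that the documents make the scenario unlikely. Animal recovery was 66.2 + 32.7 = 98.9% in rats and 79.4 + 14.4 = 93.8% in dogs (Protocol Section 4.1), both above the 90% target. The two known metabolites had exposure ratios to parent of only 0.0008 to 0.004, and accumulation on repeated dosing was minimal. This stands, and it is why the point is a safeguard.

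A reader might infer that the sampling length ignored retention. The documents do not support that: the rationale also cites nonclinical tissue-distribution and mass-balance work, which cannot be judged from here.

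A reader might also infer that retained dose cannot be told from lost excreta at all. That is too strong. Step 4 separates a 19 h decline from a week-long one, restroom access is controlled (Section 6.1), and missed or lost samples must be documented (Section 9.3.1).

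The 166 h figure is conditional, not a bound on what will happen. Excretion is expected to be mainly fecal, and the eligibility criteria allow one stool per two days, so low two-day output may reflect stool timing.

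AUC to the last quantifiable concentration, also primary, needs no extrapolation. Sections 6.3 and 9.0 already allow added procedures, and analysis detail is left to a clinical pharmacology analysis plan that is not among the documents. Those routes make the change easy, but they do not schedule the sample.

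**Conclusion.** The point holds as a conditional weakness in the design. When a subject is released with recovery below 90%, the scheduled samples can show that a slow phase exists but cannot reliably estimate its half-life or the AUC to infinity. This limits how well retained dose can be separated from incomplete collection.

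The size depends on three assumptions: the shortfall is retained, loss is first order, and residual CV is around 10%. It is nil if radioactivity follows the parent.

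Two stronger readings should be avoided. Sampling does not always end within one implied half-life: late release near 90% recovery, on the per-day reading, covers about two. Nor is half of AUC to infinity extrapolated: about 50% is the share of the slow phase alone beyond 168 h at a 166 h half-life, whereas the share of the endpoint is about 4% to 23% under the assumed intercepts.

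**What to change.** In footnote c (Protocol Section 3.0 and SAP Appendix A), add one plasma and whole-blood total-radioactivity sample at the Day 15 (±2) follow-up blood draw for subjects discharged earlier. Use its actual time in the noncompartmental analysis, as both documents already require for PK computations; the ±2-day window makes this matter. Report the result beside cumulative recovery for any subject below 90%. The discharge rule need not change.

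The cost is one extra tube per subject at an existing venepuncture and, for 6 subjects and 2 matrices, at most 12 assays, with no new visit. Section 6.3 already provides the volume, subject to the overall maximum: "Up to an additional 50 mL of blood may be drawn". A single late blood sample will not quantify dose held in tissue that blood does not reflect, so some ambiguity would remain.
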